8.3. Statistical analysis

Dose proportionality for capillary blood RSM01 PK parameters will be tested using the power regression model for AUC_{0-inf} , AUC_{0-D91} , AUC_{0-D151} , and C_{max} and, defined as:

$$\ln [\text{PK parameter}] = \beta_0 + \beta_1 \ln [\text{Dose}]$$

where the PK parameter is an AUC_{0-inf} , AUC_{0-D91} , AUC_{0-D151} , and C_{max} . The null hypothesis being tested is that the AUC and C_{max} values are dose proportional, or slope (β_1) = 1. Dose-proportionality will be concluded if the 90% CI of the slope β_1 lies entirely within $[1+\ln(0.5)/\ln(r), 1+\ln(2.0)/\ln(r)]$, where r is a ratio that describes the dose range and is defined as the ratio of highest dose/lowest dose.

Bioavailability of RSM01 following IM injection will be calculated using the ratio of geometric mean of $AUC_{0-\infty}$ and AUC_{0-D151} capillary blood RSM01 PK parameters for the comparison of IM versus IV dose. Log-transformed $AUC_{0-\infty}$ and AUC_{0-D151} estimates will be analyzed using an analysis of variance (ANOVA) model with treatment group as a factor. The parameter estimates results will be exponentiated and the ratio of geometric means and 90% CIs will be presented.

The proportion of participants with observed C_{D151} concentrations above the estimated EC90 for RSM01 (based on available pre-clinical data) will be summarized by treatment group. Exact 95% confidence interval will be calculated on the percentages.

The same analyses will be performed for venous serum (exploratory objective).

8.4. Pharmacodynamic Concentrations

Whole blood samples on VAMS and serum samples will be collected for measurement of RSV neutralizing antibody concentrations in capillary blood and venous serum.

A listing will be prepared for each cohort with both serum and VAMS data.

9. Safety Analysis

All safety summaries and analyses will be based upon the safety population.

9.1 Adverse Events

9.1.1 Adverse Events Definitions and Reporting

An adverse event (AE) is defined as any untoward medical occurrence in a patient or clinical study participant, temporally associated with the use of study intervention, whether or not considered related to the study intervention.

A treatment-emergent AE (TEAE) is defined as any event not present before study intervention administration or any event already present that worsens in severity or frequency after study intervention administration.

A serious AE (SAE) is defined as any AE that results in any of the following outcomes: death, a life-threatening AE, inpatient hospitalization or prolongation of existing hospitalization, a persistent or significant incapacity or substantial disruption of the ability to conduct normal activities of daily living, or a congenital anomaly or birth defect. Important medical events that may not result in death, be life threatening, or require hospitalization may be considered serious when, based upon appropriate medical judgment, they may jeopardize the participant and may require medical or surgical intervention to prevent one of the outcomes listed in this definition.

An AE of special interest (AESI) is a preidentified and predefined event that has the potential to be causally associated with a study intervention that the sponsor will carefully monitor.

The AE's relationship to study treatment will be evaluated by the investigator or medically qualified designee (ie, investigator, study physician). The following relationships will be collected on eCRF: related, not related.

The severity of AEs will be classified by the investigator as mild, moderate, severe or potentially life threatening. An overall AE summary will be generated presenting the frequency and percentage of participants and the number of AEs for the following:

- Any TEAE
- Any treatment-related TEAE
- Any grade 1 TEAE
- Any grade 2 TEAE
- Any grade 3 or higher TEAE
- Any treatment-related grade 3 or higher TEAE
- Any SAE
- Any treatment-related SAE
- Any TEAE leading to dose interruption (IV route of administration)
- Any TEAE leading to study withdrawal
- Any death
- Any AESI

All AEs will be coded using MedDRA (version to be delineated in the CSR). The TEAEs will also be summarized by system organ class (SOC), preferred term (PT), by severity and relationship to study treatment.

The TEAE summary tables will be sorted by SOC and PT. System organ class will be displayed in descending order of overall frequency then alphabetically. Preferred term will be displayed in descending order of overall frequency and then alphabetically within SOC. A participant with 2 or more events within the same level of summarization will be counted only once in that level using the most severe incident or most related incident. Percentages will be based on the number of participants in the safety population (unsolicited AE) or the number of participants in the safety population that had submitted any data for a solicited AE (solicited AE).

All AEs will be presented in a data listing. Separate data listings will be generated for Severe or Life-threatening AEs, treatment-related AEs, SAEs, AEs leading to study discontinuation, Fatal AEs, AESIs, as well as a listing describing a potential association of AE with immunogenicity (ADA status).

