### **8.1.9. Diary Card, Memory Aid and Daily Monitoring**

#### **Diary card**

Before leaving the clinic after dosing and completion of the post-dosing on-site confinement, participants will be given a diary card and receive guidance on how to fill in the card. All participants will receive a digital thermometer to record temperature. Participants who receive an IM dose will also receive a ruler to measure diameter of redness and/or swelling at the injection site, if present.

The diary card will be used by the study participants to record the duration, and intensity (refer to Section 8.2.3.1) of solicited injection site AEs (for participants who receive an IM dose) and solicited systemic AEs up to Day 7 following injection or infusion for all participants. This information should be recorded in the participant diary card at approximately the same time each evening, through Day 7 (refer to Section 8.2 for more information).

The diary card will be collected and reviewed by the investigator (or designee) on the Day 8 Visit for both the Dose Escalation Phase and the Dose Expansion Phase participants.

No changes to the diary card will be permitted; however, any verbally recalled information provided by the participant during review of the diary card will be documented in the source document and reported as an AE as applicable.

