## 8.2. Adverse Events and Serious Adverse Events

Local injection site solicited AEs will include pain, redness and swelling, and will be assessed after dosing at Visit 1 for 7 days (IM recipients only). If more than 1 injection is given, reactions will be assessed separately at each injection site.

Systemic solicited AEs will be assessed in all participants after dosing at Visit 1 and recorded for 7 days. These will include fever, headache, fatigue, muscle aches, nausea, vomiting, diarrhea, and joint pain.

Site staff will document any AEs in the study source during the confinement for all cohorts. The site staff will record solicited injection site AEs (IM doses only) and solicited systemic AEs (all participants), including duration and intensity, during confinement. Refer to Section 8.1.9 for solicited AEs to be recorded in the diary card by participants, through Day 7.

Solicited AEs that continue beyond Day 7 will be captured in the unsolicited AEs memory aid and marked as continuation of solicited AE. Participants will be asked to record events at the same time each evening.

Unsolicited AEs including AESIs, SAEs, and safety laboratory parameters Grade 1 and above will be collected from screening through Day 151 and recorded in the AE log by the study team.

The definitions of AEs, SAEs, serious adverse drug reactions (ADRs) and AESIs can be found in Appendix 2, Section 10.2.1, and 10.2.2, 10.2.3, 10.2.4, respectively.

Refer to Appendix 2, Section 10.2 for details regarding AEs, AESIs, and SAEs and Section 10.4 (Table 9) for laboratory parameters.

Immediate safety concerns should be discussed with the sponsor, and the SRT. The SRT will trigger an IDMC review if any pausing rule is met (see Section 8.2.7 for IDMC and Section 10.2.5 for details regarding AE reporting and follow-up).

AEs will be reported by the participant (or, as appropriate, the participant's legally authorized representative). Clinical chemistry and/or hematology results may also qualify as AEs (Section 10.4, Appendix 4).

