#### **Solicited Local and Systemic AEs**

All solicited local AEs will be considered study intervention-related events and will be summarized for each injection site.

All solicited AEs collected from Day 1 through Day 7 will be collected and summarized as described below.

The number and percentage of participants who experience one or more solicited AE will be summarized for each solicited AE, by treatment group, and by intensity, by day after study intervention administration, and overall. The first onset of each AE, and the total number of days a participant experienced each AE will also be summarized. For participants with more than 1 episode of the same event, the AE with maximum severity will be used for tabulations.

Exact 95% confidence intervals will be calculated on the percentages.

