9.1.3 Solicited Local and Systemic AEs

Local injection site solicited AEs include pain, redness and swelling. If more than 1 injection is given, reactions are to be assessed separately at each injection site. All solicited local AEs will be considered study intervention related events and will be summarized for each injection site.

Systemic solicited AEs include fever, headache, tiredness, joint pain, muscle pain, nausea, vomiting and diarrhea.

All solicited AEs collected from Day 1 through Day 7 will be collected and summarized as described below.

The number and percentage of participants who experience one or more solicited AE will be summarized for each solicited AE, by treatment group, and by severity, by day after study intervention administration, and overall. The first onset of each AE, and the total number of days a participant experienced each AE will also be summarized. For participants with more than 1 episode of the same event, the maximum severity will be used for tabulations.

Exact 95% confidence intervals will be calculated on the percentages.

Solicited local and systemic AEs will be presented in separate data listings. Ongoing AE 7 days after dosing will also be listed.

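### By-day solicited-AE percentages have no day-specific denominator, so on a literal reading a day with no entry counts as symptom-free

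*SAP*

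**What the plan says.** The only denominator rule for solicited AEs is in SAP 9.1.1: percentages are based on "the number of participants in the safety population that had submitted any data for a solicited AE (solicited AE". The unit is the participant, and no day is mentioned.

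SAP 9.1.3 sets the window: "All solicited AEs collected from Day 1 through Day 7 will be collected and summarized as described below". Each solicited AE is tabulated "by treatment group, and by severity, by day after study intervention administration, and overall", and "Exact 95% confidence intervals will be calculated on the percentages". Protocol 9.3.1 plans the same breakdown ("by treatment group, and by intensity, by day after study intervention administration, and overall") and also gives no denominator for a single day.

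The data come from two sources. On site, "The site staff will record solicited injection site AEs (IM doses only) and solicited systemic AEs (all participants), including duration and intensity, during confinement" (protocol 8.2). After discharge the participant keeps a diary: "This information should be recorded in the participant diary card at approximately the same time each evening, through Day 7" (protocol 8.1.9). The diary is reviewed at the Day 8 visit, and events recalled then are documented in source and reported as AEs where applicable.

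Protocol 9.3 says the SAP will set out how missing data are handled. SAP 4.1 does this only for AE dates and medication dates. Neither document says how a diary day with no entry is treated.

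**The concern.** Solicited AEs are primary endpoints in a first-in-human study, and the by-day table is where a reader looks for the time course of reactogenicity. A participant qualifies for the denominator through any solicited data at all, and staff recording on Day 1 normally supplies that. Once in, the participant stays in on every later day. If there is no entry for Day 5, that person cannot be in the Day 5 numerator but is still in the Day 5 denominator, which makes them a non-event.

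The error runs in one direction. A missing entry can remove an event but cannot add one, so the daily percentage cannot be too high for this reason. A daily curve could then fall over the week partly because entries stop. The confidence interval is calculated on a count that includes people who were not observed that day.

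**Working it through.** **Inputs**
- RSM01 group sizes: 6 per escalation cohort and 24 in Cohort 5 (SAP 4.2 and section 3).
- Denominator rule: SAP 9.1.1. By-day percentages with exact intervals: SAP 9.1.3.
- Number with no entry on a given day, m: not in the documents. Assumed here as 0 to 2 of 6 and 0 to 6 of 24.

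**The plan's own figures.** The plan states no figure for by-day rates. Its related figures are the chances of seeing at least one AE, 1 - (1 - p)^n:
- n = 6: p = 23.53% gives 0.800; p = 31.87% gives 0.900.
- n = 24: p = 6.49% gives 0.800; p = 9.15% gives 0.900.
- n = 48: p = 3.3% gives 0.800; p = 4.68% gives 0.900.

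All six reproduce. They take all n participants as observed.

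**Effect of the denominator.** Let N participants have any solicited data, m of them have no entry on the day, and x of the remaining N - m report the AE.
- Literal SAP rule: x/N.
- Day-specific rule: x/(N - m).
- Relation: x/N = [x/(N - m)] × (1 - m/N).

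Clopper-Pearson 95% intervals are in brackets:

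| N | m | x | Literal rule, x/N | Day-specific, x/(N - m) | Ratio |
|---|---|---|---|---|---|
| 6 | 1 | 1 | 16.7% (0.4-64.1) | 20.0% (0.5-71.6) | 0.833 |
| 6 | 1 | 2 | 33.3% (4.3-77.7) | 40.0% (5.3-85.3) | 0.833 |
| 6 | 2 | 1 | 16.7% (0.4-64.1) | 25.0% (0.6-80.6) | 0.667 |
| 24 | 2 | 3 | 12.5% (2.7-32.4) | 13.6% (2.9-34.9) | 0.917 |
| 24 | 4 | 6 | 25.0% (9.8-46.7) | 30.0% (11.9-54.3) | 0.833 |
| 24 | 6 | 3 | 12.5% (2.7-32.4) | 16.7% (3.6-41.4) | 0.750 |

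At m = 0 the two rules agree. For 24 participants with m = 4 and x = 6, the interval width is 46.7 - 9.8 = 36.9 points under the literal rule and 54.3 - 11.9 = 42.4 points on those observed.

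**Where the literal rule sits.** With complete data the rate would lie between x/N (all m symptom-free) and (x + m)/N (all m with the event). For N = 24, m = 4, x = 6 that is 6/24 = 25.0% to 10/24 = 41.7%. For N = 6, m = 1, x = 2 it is 2/6 = 33.3% to 3/6 = 50.0%. The literal rule always reports the lower end.

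**Expected size if entries are missing at random.** A daily rate of 20% is reported on average as 20% × (1 - f): 19%, 18%, 16% and 14% for f = 5%, 10%, 20% and 30%.

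**Which days are exposed.** In Cohorts 1-4 staff record through confinement to Day 3, and the schedules in both documents mark solicited-AE recording again at Visit 4 (Day 6 ± 1). Of Days 4-7, at most three have no scheduled staff recording. Cohort 5 participants may leave 4 hours after dosing, with an optional overnight stay, and their next scheduled visit is Day 8. Up to six of the seven days (Days 2-7) then depend on the diary.

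**The case against.** The best reply is that the plan leaves the by-day denominator open and does not fix a wrong one. The sentence in SAP 9.1.1 closes a paragraph about tables by system organ class and preferred term, while the by-day tables are in 9.1.3, which names no denominator. A programmer could sensibly use a day-specific n. Submitting data could also be taken to mean handing in a diary, so that a lost diary would drop out. This is fair, but 9.1.1 states the only rule for solicited AEs and nothing overrides it. Even on the diary reading, a partly completed diary leaves its blank days in the denominator. Readings that produce different tables for a primary endpoint need one settled wording.

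Other points stand as limits. Recall at the Day 8 review may recover events. The trial is descriptive, and the intervals in a group of 6 are so wide that 2/6 and 2/5 support much the same conclusion.

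A reader might also infer more than the documents support:
- That the home diary is the only source after Day 3 in Cohorts 1-4. Visit 4 contradicts this.
- That the rule excludes nobody. It has a real use: it drops IV recipients, who give no local-reaction data, from local-AE rows in the pooled columns.
- That 2/5 is the true rate. It is the observed rate; if the sixth participant was symptom-free, 2/6 is right.
- That the denominator makes the two phases' curves incomparable. Their ascertainment differs by design, and changing the denominator would not cure that.

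One could doubt that a day-specific n can be derived, since the protocol describes the diary in terms of duration and intensity. That doubt is weak: the SAP already plans by-day and number-of-days summaries from the same data.

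**Conclusion.** The point holds as a gap in the by-day analysis that should be closed before the tables are programmed. Followed literally, the SAP treats an unrecorded day as an observed negative. The reported daily rate is scaled by (1 - fraction with no entry), and its interval is too narrow for the number observed. One of 6 or four of 24 missing each scale the rate by 0.833.

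This rests on three conditions: the literal reading of SAP 9.1.1, some diary days without an entry, and no recalled event filling those days. The missing-entry fraction is assumed throughout. With complete diaries the effect is nil. It is likely to be largest in Cohort 5 and smaller in Cohorts 1-4.

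The effect is descriptive: no hypothesis test, sample-size figure or pausing rule changes. The participant-level denominator remains acceptable for overall Day 1-7 incidence, although missed days can hide events there too.

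**What to change.** In SAP 9.1.1 and 9.1.3:
- Base each by-day percentage and its exact interval on participants with a recorded entry for that solicited AE on that day. An entry may come from staff source or the diary, and includes recalled information assigned to that day.
- Print that n for every day.
- State that a day with no entry is missing, not negative.
- Keep the existing participant-level denominator for overall Day 1-7 incidence, and report how many participants have fewer than 7 completed days.
- Do not make inclusion depend on having a recorded event. Among people without a diary, that would keep those with an early event and drop those observed event-free, which pushes incidence up.

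The cost is a few sentences in the SAP and one extra n row per table. Daily intervals become slightly wider where entries are missing. No additional data collection is foreseen, because the by-day and number-of-days summaries already need a record per day; confirm against the data capture form that a day without symptoms can be told apart from a blank one.

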9.1.2 Adverse Events of Special Interest (AESI)

The following AEs will be collected and reported as AESIs: anaphylaxis or hypersensitivity reactions and infusion reactions resulting in permanent discontinuation of infusion in IV recipients.

9.1.3 Solicited Local and Systemic AEs

Local injection site solicited AEs include pain, redness and swelling. If more than 1 injection is given, reactions are to be assessed separately at each injection site. All solicited local AEs will be considered study intervention related events and will be summarized for each injection site.

Systemic solicited AEs include fever, headache, tiredness, joint pain, muscle pain, nausea, vomiting and diarrhea.

All solicited AEs collected from Day 1 through Day 7 will be collected and summarized as described below.

The number and percentage of participants who experience one or more solicited AE will be summarized for each solicited AE, by treatment group, and by severity, by day after study intervention administration, and overall. The first onset of each AE, and the total number of days a participant experienced each AE will also be summarized. For participants with more than 1 episode of the same event, the maximum severity will be used for tabulations.

Exact 95% confidence intervals will be calculated on the percentages.

Solicited local and systemic AEs will be presented in separate data listings. Ongoing AE 7 days after dosing will also be listed.

9.1.4 Unsolicited Treatment Emergent AEs, SAEs, and AESI

All unsolicited AEs, SAEs, and AESIs will be recorded from screening through Day 151.

Unsolicited AEs, SAEs, and AESIs will be coded according to MedDRA and summarized by System Organ Class (SOC), Preferred Term (PT) and highest severity. Clopper-Pearson exact 95% CIs will be calculated on the percentages of participants with AESIs. AEs leading to dose interruption for cohorts with IV route of administration and AEs leading to withdrawal from the study will also be summarized.

The number of events reported, the number of participants and percentage of participants who experience one or more unsolicited AE through Day 151, and one or more SAE, and one or more AESI from screening through Day 151 will be summarized by treatment group, as appropriate, and across all RSM01 dose levels and routes of administration, combined. The severity of each AE, and relationship between the AE and study intervention, will also be summarized.

For participants with more than 1 episode of the same event, the maximum severity will be used for tabulations. Participants reporting more than one occurrence for the PT term level being summarized will be counted only once.

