### 8.2.1. Time Period and Frequency for Collecting AE and SAE Information

Type of Event	Collection Time Period
All solicited AEs	Day 1 through Day 7 (inclusive)
Unsolicited AEs, and SAEs including AESIs	Screening through end of study (Day 151)

Distribution and collection days for diary cards and memory aids are shown in the SoA.

Medical conditions that begin before the start of study intervention but after obtaining informed consent will be recorded on the Medical History/Current Medical Conditions section of the CRF, not in the AE section.

All SAEs and AESIs will be reported to the sponsor or designee within 24 hours, as indicated in Appendix 2, Section 10.2.6. The investigator will submit any updated SAE and AESI data to the sponsor or designees within 24 hours of it being available.

Investigators are not obligated to actively seek AEs, SAEs or AESIs after a participant concludes study participation. However, if the investigator learns of any SAE, including a death, at any time after a participant has been discharged from the study, and he/she considers the event to be related to the study intervention or study participation, the investigator must notify the sponsor or designee within 24 hours.

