#### **Unsolicited Treatment Emergent AEs, SAEs and AESI**

All unsolicited AEs, serious adverse events (SAEs), and/or AESI will be recorded from screening through Day 151.

Unsolicited AEs, SAEs, AESI will be coded according to the Medical Dictionary for Regulatory Activities (MedDRA) and summarized by System Organ Class (SOC), Preferred Term (PT) and greatest intensity. Clopper-Pearson exact 95% CIs will be calculated on the percentages. AEs leading to withdrawal from the study will also be summarized.

The number of events reported, the number of participants and percentage of participants who experience one or more unsolicited AE through Day 151, one or more SAE, and/or one or more AESI from screening through Day 151 will be summarized by treatment group, as appropriate, and across all RSM01 dose levels and routes of administration, combined. The intensity of each AE, and relationship between the AE and study intervention, will also be summarized.

For participants with more than 1 episode of the same event, the AE with maximum intensity will be used for tabulations. Participants reporting more than one occurrence for the PT term level being summarized will be counted only once.

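### SAP 9.1.4 counts SAEs and AESIs by treatment group from screening, so a pre-dose event in a dosed participant would be charged to a treatment not yet given; a counting rule for solicited reactions running past Day 7 is also missing.

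*SAP*

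**What the plan says.** **SAEs and AESIs.** The counting sentence in SAP 9.1.4 reads "and one or more SAE, and one or more AESI from screening through Day 151 will be summarized by treatment group". Protocol 9.3.1 agrees: "one or more AESI from screening through Day 151 will be summarized by treatment group". In both documents the recording window is given in a separate sentence, so this one sets what is counted. In the SAP 9.1.1 overview, several rows are explicitly TEAE rows, but *Any SAE* and *Any AESI* are not.

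The SAP section is nevertheless titled "9.1.4 Unsolicited Treatment Emergent AEs, SAEs, and AESI", and SAP 9.1.1 states: "A treatment-emergent AE (TEAE) is defined as any event not present before study intervention administration", adding events already present that worsen after dosing.

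**Where pre-dose events are recorded.** The table in protocol 8.2.1 collects unsolicited AEs, SAEs and AESIs from screening. The text below it says: "Medical conditions that begin before the start of study intervention but after obtaining informed consent will be recorded on the Medical History", and keeps them out of the AE section of the CRF. Protocol 8.2 has these events entered in the AE log from screening, and both Schedules of Activities mark AE, AESI and SAE recording at the screening and Day -1 visits.

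**Solicited AEs lasting past Day 7.** Protocol 8.2: "Solicited AEs that continue beyond Day 7 will be captured in the unsolicited AEs memory aid and marked as continuation of solicited AE". SAP 9.1.3 summarises solicited AEs collected on Days 1 to 7, says that "the total number of days a participant experienced each AE will also be summarized", and lists those still ongoing after 7 days.

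**The concern.** A by-treatment safety count should contain only events that the treatment could have influenced. Under the stated window, an SAE or hypersensitivity AESI arising between consent and dosing enters the numerator of whichever arm the participant later joins. The plan also contains text pointing the other way, so two programmers following it in good faith could produce different tables.

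This matters because SAEs, AESIs, unsolicited AEs and solicited AEs to their stated days are the primary endpoints. The trial is descriptive, so the counts themselves are the result. Arms are small: six on RSM01 in each escalation cohort and eight on placebo in all.

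The continuation of solicited reactions is a lesser matter of the same kind. A reaction that starts after dosing and persists meets the TEAE definition, so the treatment-emergent filter would not keep its continuation record out of the unsolicited tables. No other rule says what to do with it.

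**Working it through.** **1. The plan's own figures.** SAP 4.2 gives the probability of seeing at least one AE, 1 − (1 − p)^n:

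- n = 6: p = 23.53% gives 0.800; p = 31.87% gives 0.900.
- n = 24: p = 6.49% gives 0.800; p = 9.15% gives 0.900.
- n = 48: p = 3.3% gives 0.800; p = 4.68% gives 0.900.

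All six reproduce and none depends on the counting window.

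**2. The SAE/AESI texts side by side.**

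- Pointing to inclusion of pre-dose events: the counting sentences in SAP 9.1.4 and protocol 9.3.1; the unqualified overview rows in SAP 9.1.1; and recording from screening in protocol 8.2, the 8.2.1 table and both Schedules of Activities.
- Pointing to exclusion: the SAP 9.1.4 and protocol headings, the TEAE definition, and the Medical History sentence in protocol 8.2.1.

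The second group contradicts the first but does not override it. An explicit counting window is more specific than a heading. The TEAE tables by system organ class and preferred term are separate from the SAE and AESI participant counts.

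**3. Reach of the window.** Screening and Day -1 take at most 30 days and follow-up is 151 days, so pre-dose time is at most 30/(30 + 151) = 16.6% of the SAE/AESI window. This is a share of time, not an event rate.

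**4. One misplaced participant (assumed).** With Clopper-Pearson 95% intervals:

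| Group | Event excluded | Event counted |
|---|---|---|
| n = 6 | 0% (0 to 45.9) | 16.7% (0.4 to 64.1) |
| Placebo, n = 8 | 0% (0 to 36.9) | 12.5% (0.3 to 52.7) |
| n = 24 | 0% (0 to 14.2) | 4.2% (0.1 to 21.1) |
| All RSM01, n = 48 | 0% (0 to 7.4) | 2.1% (0.1 to 11.1) |

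**5. A range under a constant background rate (assumed).** If r is the risk over 151 days, the risk over 181 days is 1 − (1 − r)^(181/151). For r = 1%, 2%, 5% and 10% this gives 1.2%, 2.4%, 6.0% and 11.9%. The chance of at least one such participant among 48 rises from 38% to 44%, 62% to 69%, 92% to 95%, and 99.4% to 99.8%. These shifts lean high: they use the full 30 days, and they ignore that a healthy volunteer with a pre-dose SAE may never be dosed.

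**6. Continuing solicited reactions.** Take a headache on Days 6 to 10. If the continuation is joined to its episode, it is one solicited event of 5 days. If the solicited summary uses Days 1 to 7 only and the marked record goes into the unsolicited tables, it is a solicited event of 2 days plus an unsolicited TEAE. The SAP does not say which applies. Its count-once rule works within a level of summarisation, so it would not remove a duplicate lying between the solicited and unsolicited tables.

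**The case against.** The best defence is that the documents largely define pre-dose events out. Protocol 10.2.1 ties an AE in time to use of the study intervention, 10.2.2 says that something which is not an AE cannot be an SAE, and 10.2.4 makes AESIs a kind of AE. SAP 4.1.1 imputes AE start dates precisely to decide treatment emergence. If the Medical History sentence in protocol 8.2.1 is followed, pre-dose conditions never reach the AE data. Safety tables cover only dosed participants, so a pre-dose SAE would have to occur in a volunteer who still passed the Day -1 and Day 1 eligibility checks. An infusion-reaction AESI cannot precede dosing.

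This stands as an argument that such events will be rare, and that entry of pre-dose events is possible rather than established. It does not remove the stated counting window, and the same protocol records AEs, SAEs and AESIs from screening in several places.

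On continuations, the defence is stronger. The records carry a mark identifying them as solicited, ongoing reactions are listed, SAP 9.1.3 states no cap on total days, and protocol 10.2.5 takes the resolution date as the last day the participant had the event. A reader might infer that the plan counts these episodes twice and cuts their duration at Day 7. The documents state neither; they leave both open. Joining the records is also not wholly free: under protocol 8.2 and 8.2.3.1, local solicited reactions outside confinement are graded by the participant, whereas unsolicited intensity is the investigator's assessment.

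**Conclusion.** The SAE/AESI counting rule is wrong as written and should be changed. SAP 9.1.4 and protocol 9.3.1 open the by-treatment count at screening, against their own treatment-emergent framing, and the SAP 9.1.1 overview does not correct it.

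The point is limited in three ways. First, a reader might infer that all unsolicited-event counts take in pre-dose events. They do not: in the counting sentence the screening start belongs to the SAEs and AESIs, and unsolicited AEs fall under the TEAE definition. Second, a reader might infer that the primary counts will be inflated by a known amount. The documents give no pre-dose or carry-over rate, so the figures above are illustrations resting on one assumed participant or an assumed constant rate. The number of participants affected may well be zero. Third, the handling of solicited reactions past Day 7 is a missing rule, and calls for clarification rather than correction.

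The change is still worth making because the arms are small and the descriptive counts are the primary result. The sample-size statements are unaffected.

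**What to change.** - **SAP 9.1.1 and 9.1.4, and protocol 9.3.1:** count by treatment group only SAEs and AESIs with onset or worsening on or after study intervention. List pre-dose events separately. Relabel the two overview rows to match.
- **Protocol 8.2.1:** reconcile the collection table with the text beneath it, and align protocol 8.2 and the Schedules of Activities, so that there is one place where a pre-dose event is recorded.
- **SAP 9.1.3 and 9.1.4 (clarification):** state that records marked as continuations stay with their solicited episode, are excluded from unsolicited participant and event counts, and that total days runs to the recorded resolution date. State whose grade applies after Day 7.

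The cost is a few lines of SAP text and two programming flags, using the continuation mark and onset dates that are already collected. No new data are needed. Protocol 10.1.6 lets the analysis plan carry changes to analyses, so the SAP can be corrected first and the protocol wording aligned with it.
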